9.9 Safety Analyses

Not applicable.

9.10 Interim Analyses

Not applicable.

10 NON-OPPOSITION PROCESS

The Investigator shall contact eligible subjects regarding the investigation and if they are interested in taking part, a non-opposition form containing all relevant study information will be sent to them via mail or shared at the clinic if a follow-up appointment is planned. The rationale of the clinical investigation, as well as the risks and benefits, what participation will involve, and alternatives to participation will be explained to the subject. Ample time will be provided for the subject to enquire about details of the clinical investigation and to decide whether to participate.

All questions about the clinical investigation shall be answered to the satisfaction of the subject. Subjects shall not be coerced or unduly influenced to non-oppose participation or to continue to participate in a clinical investigation.

If the subject is not opposed to participating in the investigation, the date of the discussion must be recorded in the subject's medical records as well as in the non-opposition form and will be used as the date of enrolment. This process needs to be done prior to any data collection for the purpose of this investigation. A copy of the non-opposition form, signed by the investigator, will be shared with the subject, either at the clinic or by registered mail, together with the questionnaire. The original signed non-opposition form shall be archived in the Investigator's Site File at the investigational site. The subject shall be informed in a timely manner if new information becomes available that may be relevant to the subject's willingness to continue participation in the clinical investigation. The communication of this information must be documented as an update to the non-opposition form and confirmation of non-opposition of the subject.

11 ADVERSE EVENTS AND DEVICE DEFICIENCIES

Not applicable

12 DEVICE ACCOUNTABILITY

Not applicable.

13 DEVIATIONS FROM THE CLINICAL INVESTIGATION PLAN

The Investigator(s) must not deviate from the CIP, except in case of an emergency to protect the safety and well-being of the subject(s). Such deviations will be documented by the site personnel in the source documentation for the subject and reported to the relevant EC as per institutional requirements and to the Sponsor as soon as possible.

If there is a deviation from CIP-defined assessments or parts thereof are omitted or completed incorrectly, the deviation will also be documented by the site personnel in the source documentation for the subject. Depending on the type or severity of the deviation the Investigator may be required to notify the EC.

All CIP deviations will be documented in the eCRF to enable analysis and reporting by the Sponsor in the Clinical Investigation Report (CIR), or to the relevant regulatory authority(s), if applicable.

Gross misconduct on behalf of an Investigator, such as intentional non-compliance with CIP or GCP requirements or fraud, will result in disqualification of the Principal Investigator and/or Investigational Site from participation in the investigation. Data provided by the Principal Investigator or Investigational Site will be excluded from the per-protocol analysis group.

14 DATA MANAGEMENT

The CRF will capture the datapoints necessary to determine the subject status according to the criteria described in section 7.2.5.

Source data will be captured in clinic notes, paper-based source data worksheets, or printed directly from testing software. If electronic medical records do not permit read only access for monitoring purposes, a certified printout must be provided. ECAP measurements made using CustomSound EP will be processed by the sponsor. The anonymised CustomSound database records (CDX files) will be provided to the sponsor via upload to the data capture portal.

Data collection will be performed using [REDACTED] for electronic data capture (EDC) on electronic Case Report Forms (eCRFs). Site staff will be trained on the completion of the eCRFs prior to obtaining access to the system and will have their own Login/Password. Access to clinical study information will be based on an individual's role and responsibilities.

[REDACTED] uses role-based user permissions for data entry, viewing, and reporting options. All communications between users and the EDC server are encrypted. Web servers are protected by a managed firewall. This application is designed to be in compliance with applicable regulations including 21 CFR Part 11.

The application will include programmed data consistency checks and supports manual generation of data clarifications/queries, including documentation of site responses. The application maintains a

comprehensive audit trail for all data entered, including updates and queries, and documents the time that each entry occurred and who made the entry.

Principal Investigators will affirm that the data for each subject at their site is accurate and complete by way of an electronic signature.

In addition, de-identified electronically generated data will be collected from CustomSound clinical fitting software and electrophysiology software. The unamended data file shall be regarded as the source.

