7.2.7.1 Blinding Procedures

Not applicable.

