7.3.3.4 ECAP-based bottom-up tests (post-surgery)

Specific ECAP-based standard tests of bottom-up processing were established at the centre. Firstly, automatic ECAP thresholds using "AutoNRT" are measured for each intracochlear electrode using default parameters. Then one basal electrode (number 8) and one apical electrode (16) is used for subsequent tests. If there is no AutoNRT response on one of these electrodes, then an adjacent one

is used. All subsequent ECAP testing uses the forward masking artifact reduction technique with equal masker and probe levels.

Firstly, a negative-leading AGF is measured up until 220 CL or the subject indicates that the sound is too loud. Then an AGF is measured using the positive-leading polarity pulses.

The CL to obtain 100 μ V is determined from the standard AGF, or the maximum tolerable CL if 100 μ V was not obtained. This CL is used for subsequent recovery function and SOE tests.

Recovery functions are obtained using a standard sequence of masker-probe intervals and the CustomSound EP software computes the absolute and relative refractory periods.

SOE functions are obtained using a specific sequence of maskers so reduce overall test time. The maskers span 14 electrode locations but not all locations are used. The CustomSound EP software computes the 50% maximum amplitude width (in electrodes). The area under the curve can be computed manually (up to 14 electrode units).

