9.2 Endpoints

9.2.1 Primary Endpoint

Good or poor performer based on sentence recognition score at 1-month $\geq 90/100$ or $< 90/100$. Good/poor performer status will be compared to pass/fail on the processing parameter tests. (binary classification)

"Fail" status on the processing parameter tests is established as:

- MoCA: score <26/30.
- Stroop test: score below the confidence interval for age 50 years with elementary education, or one or more corrected or non-corrected errors are noted.
- ÉCLA-16+ subtests 3 or 4: one or two scores below normal range, or time taken greater than established confidence intervals.
- Aided thresholds: more than two of five thresholds greater than 30 dB SPL.

The following will be extracted from the CustomSound software database records:

- Datalogging: None-use is defined as less than 2 hours' average time-on-air per day between activation and 1-month (mean -2 standard deviations re. data of Holder et al, 2020).
- AutoNRT: Absent for more than six electrodes. Inability to run AutoNRT or all of the following three NRT tests due to lack of response at maximum comfortable level or non-auditory stimulation leading to termination of the test.
- AGF polarity: For either probe electrode, a slope of negative leading significantly smaller than positive leading, and less than 70% of positive leading.
- Recovery function: For either probe electrode, a relative or absolute recovery period significantly longer than the confidence interval for normal range (Tabibi et al, 2019).
- Spread-of-excitation: For either probe electrode, greater than 35% area under the curve (>5 across the 14-electrode range).

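### The sponsor processes the ECAP data and also receives the sentence scores, and nothing in the plan masks that processing or fixes ECAP pass/fail before the two are linked

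*Combined protocol and SAP*

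**What the plan says.** - **Primary analysis (9.3.1, 9.6).** One 2x2 table sets good/poor performer status against battery pass/fail. It is tested by chi-squared at 0.05, or by Fisher's exact test if a cell is too small. Under 7.2.3 a single failed test fails the battery.
- **Fail criteria (9.2.1).** There are nine, and four use ECAP data. AutoNRT is a count: "AutoNRT: Absent for more than six electrodes", with a further clause for tests that could not be run. AGF polarity requires "a slope of negative leading significantly smaller than positive leading, and less than 70% of positive leading". Recovery requires "a relative or absolute recovery period significantly longer than the confidence interval for normal range". SOE fails above 35% of the area, which the same line also gives as more than 5 on a 14-electrode range.
- **Derivation (7.3.3.4).** AutoNRT thresholds are automatic. The software returns both refractory periods and the SOE half-maximum width. The fail rule uses the SOE area instead, and for that the text says "The area under the curve can be computed manually (up to 14 electrode units". No software output or fitting method is named for the AGF slope.
- **Who handles the data.** Section 14: "ECAP measurements made using CustomSound EP will be processed by the sponsor". Section 15: subject data reach the sponsor on CRFs. The Schedule of Events and 7.3.3.6 list the 1-month score in quiet among the data collected.
- **Masking.** The entry under "7.2.7.1 Blinding Procedures" is "Not applicable". Section 14 provides role-based EDC access and anonymised CDX uploads, but ties neither to masking.

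**The concern.** The study is retrospective, so each subject's good/poor label already exists when the ECAP files are processed. One axis of the primary table is then derived, at least in part, within an organisation that also holds the other axis. Where a criterion leaves a choice, such as how to compute an area, which slope fit to use or what counts as significant, a reader who knows the outcome can resolve borderline cases toward it, even unintentionally. That would build in the association the study sets out to confirm, and a significant result could not be told apart from outcome-aware scoring.

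**Working it through.** **1. The plan's own figure.** Inputs: N = 30, sensitivity and specificity about 80%, splits 50/50 and 40/60 (7.2.3, 9.4). The fail probability is therefore 0.20 in good and 0.80 in poor performers. Summing the two binomials over all tables rejected at 0.05 gives power of 0.94 (chi-squared) and 0.87 (Fisher) at 15/15, and 0.94 and 0.88 at 12/18. The stated >80% is reproduced. The concern is about bias and does not touch the sample size.

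**2. Where judgement can enter.**

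| ECAP criterion | Derived by | What is left open |
|---|---|---|
| AutoNRT | Automatic; a count | Little; tests were stopped in clinic |
| AGF polarity | Two slopes; method not stated | Slope fit; test behind *significantly* |
| Recovery | Periods from software | Test behind *significantly* |
| SOE | Area, may be manual; by whom not stated | Calculation; cut-off 0.35 × 14 = 4.9, or 5 (5/14 = 35.7%) |

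Three of the nine criteria therefore carry most of the room.

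**3. Effect of shifted readings (illustrative).** Start from no association with 12 good and 18 poor performers: 6/12 and 9/18 fail. The uncorrected statistic is N(ad − bc)² / (product of the four margins).

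| Fails, good vs poor | Shift | Chi-squared p | Fisher p |
|---|---|---|---|
| 3/12 vs 12/18 | 3 down, 3 up | 30 × 90² / 48,600 = 5.00; 0.025 | 0.060 |
| 2/12 vs 13/18 | 4 down, 4 up | 30 × 120² / 48,600 = 8.89; 0.003 | 0.008 |
| 4/12 vs 13/18 | 2 down, 4 up | 30 × 84² / 47,736 = 4.43; 0.035 | 0.061 |
| 6/12 vs 15/18 | 0 down, 6 up | 30 × 72² / 40,824 = 3.81; 0.051 | 0.10 |
| 6/12 vs 16/18 | 0 down, 7 up | 30 × 84² / 38,016 = 5.57; 0.018 | 0.034 |

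**4. How many good performers could move down.** A fail becomes a pass only if every other test is passed. Assume nine independent, equally likely criteria and a 50% battery fail rate; neither assumption is in the documents. Failing through ECAP criteria alone then has probability 0.5^(5/9) − 0.5 = 0.680 − 0.5 = 0.180, or 12 × 0.180 = 2.2 of 12 good performers. Through the three open criteria alone it is 0.5^(6/9) − 0.5 = 0.630 − 0.5 = 0.130, or 1.6 of 12. These are ceilings, before asking whether any such curve is borderline. Three or four downward shifts are therefore more than one would expect to be available.

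**5. Type I error under an assumed bias.** Let a fraction x of movable discordant subjects be read into agreement with known status. The fail probability is 0.5 − x·m in good and 0.5 + 0.5x in poor performers, where m is the probability of a reversible fail. Ranges are over 15/15 and 12/18, using the summation in step 1.

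| x | m = 0.5 (every fail reversible): chi-squared; Fisher | m = 0.130 (three criteria only): chi-squared; Fisher |
|---|---|---|
| 0 | 0.046–0.049; 0.017–0.023 | same |
| 10% | 0.078–0.082; 0.033–0.043 | 0.059–0.063; 0.023–0.031 |
| 20% | 0.183–0.187; 0.095–0.114 | 0.099–0.106; 0.044–0.058 |

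The fail-on-any rule limits the downward moves and so roughly halves the chi-squared error at x = 20%. The documents give no value for x.

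**The case against.** Several stronger readings are tempting, and the documents do not support them.

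- **That all four ECAP criteria are scored by hand or by eye.** Only the SOE area is described as possibly manual, the text does not say who does it, and computing an area from recorded amplitudes is largely arithmetic. AutoNRT and the refractory periods are software-derived. The incomplete masker coverage was set at acquisition, and decisions to stop a test were taken in clinic, so neither gives the sponsor discretion later.
- **That the blinding entry is a decision to score unmasked.** It sits under randomisation in a study with no comparator and most naturally refers to treatment blinding. What stands is that no other section masks the scorer.
- **That section 4.1.2 is contradicted when it calls ECAP measures objective.** That sentence concerns independence from the patient's top-down processing and says nothing about masked scoring.
- **That six to eight shifted readings would be enough.** This needs three or four good performers to move from fail to pass, against the ceilings in step 4. At six shifts the result also depends on the test (chi-squared 0.025, Fisher 0.060).

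Two further limits stand. The plan says the sponsor processes ECAP measurements; that it also assigns pass/fail is a reasonable inference, not a statement. Anonymised CDX files, role-based access and an unamended source file allow results to be re-derived, which restrains undetected drift but is not masking. It is also fair to say that undefined rules are as much the problem as unmasked readers, and masking alone would not define them.

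**Conclusion.** The gap is real but narrower than it first looks. The plan permits ECAP results to be derived with the outcome in view; it does not show that this will happen. The exposure is mainly in the SOE, AGF and recovery criteria. Its direction would favour the primary hypothesis, and its size cannot be stated because the number of borderline curves is not given. The type I figures rest on an assumed bias fraction, independent and equally likely criteria, and a 50% battery fail rate, so they show sensitivity and are not an estimate. This is a cheap improvement to a single-centre feasibility study. It leaves N = 30 and the >80% power unchanged.

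**What to change.** In section 14, with a cross-reference from 7.2.7.1, state that:

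1. CDX files are processed, and ECAP pass/fail results locked, by sponsor personnel without access to sentence scores, using the existing role-based permissions.
2. ECAP results are merged with performer status only after that lock.
3. The SOE area and the AGF slopes are computed with one fixed script for all subjects.

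In 9.2.1, before any scoring, keep one SOE cut-off (35%, i.e. 4.9, or >5) and define the test meant by *significantly* in the AGF and recovery rules.

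Cost: an access setting, an ordering step and a short script, with no extra subjects or procedures. The downside is that the merged data set is available slightly later.

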15 CONFIDENTIALITY

The investigator and site staff will collect and process personal data of the subjects in accordance with governing data privacy regulations [such as the EU GDPR regulations]. Subjects have the right to access their data and request for its correction or deletion after withdrawal.

Data will be reported to the Sponsor on CRFs or related documents (for example, questionnaires). Subjects will be identified on CRFs and other related documents only by a unique subject identification code and shall not include the subject's name or other personal identifiable information. Completed CRFs or related documents are confidential and will only be available to the Investigator and site staff, the Sponsor and their representatives, and if requested to the Ethics Committee and national regulatory authorities. Publications or submission to a regulatory authority shall not disclose the identity of any subject.

16 ETHICS COMMITTEE AND REGULATORY AUTHORITY APPROVAL

The clinical investigation will not commence prior to the written favourable opinion or approval from the EC and/or regulatory authority (if appropriate) is obtained.

The final Sponsor-approved version of the CIP, the non-opposition form, and other necessary documents shall be submitted to the EC. A copy of the EC opinion/approval shall be provided to the Sponsor.

The Investigator shall forward to the Sponsor, for review and approval, any amendment made to the approved ICF and any other written information to be provided to the subject prior to submission to the EC.

The Sponsor and Principal Investigator will continue communications with the EC, as required by national regulations, the clinical investigational plan, or the responsible regulatory authority.

Any additional requirements imposed by the EC or regulatory authority will be implemented by the Sponsor.

The Investigator shall submit the appropriate documentation if any extension or renewal of the EC approval is required. In particular, substantial amendments to the CIP, the non-opposition form, or other written information provided to subjects will be approved in writing by the EC.

The Investigator shall report to the EC any new information that may affect the safety of the subjects or the conduct of the clinical investigation. The Investigator will send written status summaries of the investigation to the EC regularly, as per local EC requirements.

Upon completion of the clinical investigation, the Investigator shall provide the EC with a brief report of the outcome of the clinical investigation, as per local EC requirements.

The clinical investigation is covered by clinical trial insurance, meeting the requirements of the participating countries.

17 SUSPENSION OR PREMATURE TERMINATION

The Sponsor will discontinue the clinical investigation site if:

- 1) major non-adherence to the CIP or GCP principles is occurring
- 2) it is anticipated that the subject recruitment will not be adequate to meet the objectives of the clinical investigation

18 AMENDMENTS TO THE CLINICAL INVESTIGATION PLAN

No changes in the CIP or investigation procedures shall be made without mutual agreement of the Principal Investigator and the Sponsor. This agreement will be documented as a CIP amendment. Amendments will require notification to the Ethics Committee (EC) by the Principal Investigator (and to the relevant regulatory authority(s) by the Sponsor, if applicable).

19 RECORD KEEPING AND RETENTION

Data generated from the clinical investigation will be stored in a limited-access file area and be accessible only to representatives of the study site, the Sponsor and its representatives, and relevant health authorities/regulatory agencies. All reports and communications relating to study subjects will identify subjects only by subject unique identification code. Complete subject identification will be maintained by the Investigator. This information will be treated with strict adherence to professional standards of confidentiality.

The investigator must retain study-related records for a period of at least 15 years after completion of the investigation.

The Sponsor will notify the Principal Investigator when records are no longer needed. The Investigator will not discard any records without notifying the Sponsor. If the Principal Investigator moves from the current investigational site, the Sponsor should be notified of the name of the person who will assume responsibility for maintenance of the records at the investigational site or the new address at which the records will be stored. The Investigator will notify the Sponsor as soon as possible in the event of accidental loss or destruction of any study documentation.

20 PUBLICATION POLICY

This clinical investigation will be prospectively registered at a public clinical trial registry ClinicalTrials.gov or European equivalent if active.

A joint peer-reviewed publication authored by the clinical investigator(s) and Sponsor will be prepared. In addition, the results of the clinical investigation may also be disseminated as conference presentations (for example, abstract and poster session). Manuscript authorship and responsibilities will be discussed and agreed upon prior to investigation start and in accordance with guidelines and recommendations provided by the International Committee of Medical Journal Editors (ICMJE) to

enable communication in a timely manner. All contributors who do not meet the criteria for authorship will be listed in an acknowledgments section of the publication.

21 STATEMENTS OF COMPLIANCE

This clinical investigation shall be conducted in accordance with ethical principles that have their origin in the Declaration of Helsinki, International Standard ISO 14155 Clinical investigation of medical devices for human subjects - Good Clinical Practice, and any regional or national regulations, as applicable.

22 QUALITY CONTROL AND ASSURANCE

In accordance with Cochlear's Quality Management System, all clinical investigations shall be conducted according to internationally recognised ethical principles for the purposes of obtaining clinical safety and performance data about medical devices.

The Sponsor employees (or designee) shall use standard operating procedures (SOP) to ensure that clinical study procedures and documentation are consistently conducted and compliant with the ISO 14155 Standard, Good Clinical Practice (GCP), and applicable local regulations.

22.1 Monitoring

The Sponsor will perform on-site and remote monitoring visits as frequently as necessary to oversee conduct, data collection and record keeping by sites.

The site will receive an on-site initiation visit by the Cochlear monitor and research scientist. At least one onsite monitoring visit will be performed when >80% of patient records have been entered into the database. A close-out visit will be performed by the monitor once all patient records have been entered or marked as missing.

